## 5. Randomization will be done using Castor EDC in a 1:1 ratio and patient will be randomized in blocks of varying size between 4 and 10 patients. TREATMENT OF SUBJECTS

### 5.1 Investigational product/treatment

FlowSure is a digital hanging scale that continuously weighs urine production over time, see detailed description under paragraph 6.

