## 1. INTRODUCTION AND RATIONALE

Diuresis, the amount of hourly produced urine, is a vital parameter that is routinely measured in patients hospitalized patients. Up to half of the millions of patients hospitalized each year in nursing wards and all intensive care unit patients and those undergoing surgery have an indwelling urine catheter inserted into the bladder in order to continuously measure urine production. A reduced diuresis of for example less than 30 millilitres per hour is the first sign of hemodynamic and clinical instability of the patient that can be the result of a (occult) bleeding, infection, or heart failure.

The first response of the body to mitigate hemodynamic instability is to retain fluid by decreasing diuresis. The traditional monitors are insufficient as reading and registering diuresis manually every hour for every patient is burdensome for nurses and often deprioritized due to time constraints. Unlike most other vital parameters, diuresis cannot simply be measured instantly like heart rate or blood pressure but requires monitoring over time which complicates registration. Hourly diuresis registration often is incomplete as nurses are unable to register at set times: a nurse assisting one patient cannot register urine production at the same time of the other patients under his or her watch.

As a result, information about the vital parameter diuresis is often not available when the clinical situation of the patient deteriorates and therefore compromising the patient safety. With accurate and complete information regarding changes in diuresis that prompt automated alerts, a clinical deterioration of the patient's condition will be detected earlier and intervened upon sooner, without an extra burden/time costing intervention of the nurse.

The automated FlowSure monitor is a digital hanging scale that continuously weighs urine production over time, as urine flows through the urine catheter into the catheter bag underneath the patient's bed. FlowSure visualizes the most recent hourly urine production on the screen of the medical device and transmits the generated data to the patient's electronic medical record.

Since the specific weight of urine is equal to water and thus one gram is equal to one millilitre, the increase in weight of the urine bag over time is a surrogate for urine production.

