### 4. STUDY POPULATION

#### 4.1 Population (base)

Patient will be drawn from our hospital wards including but not limited to the general cardiology ward, cardiac care unit (CCU).

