### 4.3 Sample size calculation

Part A will consist of 25 patients. Since this is the first-in-human study, to establish safety, and initial efficacy the investigators believe that this number will provide us meaningful information to collect scientific data for further development.

Part B will consist of 25 patients monitored with a manual monitor and 25 patients monitored with the FlowSure. The completeness of hourly urine production registration between the manual urine monitor and the FlowSure was compared using a two-group comparison of proportions. The study enrolled a total of 50 patients, with 25 patients using the manual urine monitor and 25 patients using the FlowSure. The completeness rate for the manual urine monitor was approximately 50% ( $P_1 = 0.50$ ), while the FlowSure data collection demonstrated a higher completeness rate of >90% ( $P_2 = 0.90$ ).

To assess the statistical significance of the difference in completeness rates, a significance level (alpha) of 0.05 was employed. The power (1 - beta) was set at 0.8. The pooled proportion (P) was calculated to be 0.70, and the standard error (SE) was estimated as 0.0948. Using a z-score of 1.96 for the selected alpha level, the difference in completeness rates was determined to be 0.40.

The effect size (ES), calculated by dividing the difference in completeness rates by the standard error, was found to be 4.216. Consequently, the study had a power of approximately 99% to detect the assumed difference in completeness rates between the manual urine monitor and the FlowSure monitoring device.

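### Part B neither stratifies allocation by ward nor plans an analysis adjusted for ward, which may cost precision in the completeness estimate but causes no bias

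*Combined protocol and SAP*

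**What the plan says.** - **Allocation.** The text at the head of section 5 sets an equal split between the arms, generated in Castor EDC. On the blocks it states: "patient will be randomized in blocks of varying size between 4 and 10 patients". No stratification factor is named there or elsewhere.
- **Wards.** Section 4.1 recruits from more than one ward: "our hospital wards including but not limited to the general cardiology ward, cardiac care unit (CCU"). The share expected from each is not given.
- **Why manual registration is incomplete.** Section 1 calls hourly reading "burdensome for nurses and often deprioritized due to time constraints" and adds that "a nurse assisting one patient cannot register urine production at the same time of the other patients under his or her watch".
- **Size and assumed rates.** Section 4.3: "Part B will consist of 25 patients monitored with a manual monitor and 25 patients monitored with the FlowSure". Manual completeness is taken as about 50% and FlowSure as above 90%.
- **Analysis.** Section 9.1 plans an unadjusted two-group test (chi-square or Fisher). Subgroup analyses and regression are allowed as further exploratory work, also to deal with confounders, but they are optional and ward is not mentioned. Section 9.2 defines completeness as the share of hourly measurements recorded over 24 hours, which is naturally a percentage per patient.

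**The concern.** If missed readings come from nurses having too many patients, completeness in the manual arm should follow staffing. A general cardiology ward and a CCU probably differ in that respect. Ward is known before randomisation, so it can be used in both allocation and analysis, and the plan uses it in neither.

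With 25 patients per arm, the wards can fall unevenly between the arms by chance. Each such imbalance moves the estimate in that one trial, and the spread of these movements adds to its standard error. At stake are the estimated gain in completeness and its interval, more than the p-value. In a non-blinded trial of 50 patients, a visible ward imbalance would also raise the question of whether part of the difference reflects staffing. A regression chosen afterwards answers that less well than one fixed in advance.

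**Working it through.** **1. The plan's own figure.** Section 4.3 gives a standard error of 0.0948, a ratio of 4.216 and power of about 99%. The pooled formula gives √(0.70 × 0.30 × 2/25) = 0.130, not 0.0948. The 99% follows only from the stated ratio: Φ(4.216 − 1.96) = 98.8%. From 0.50 against 0.90 with 25 per arm, two-sided power is 89.5% (pooled), 92.9% (unpooled) or 83.3% (exact Fisher). That mismatch is a separate matter. Here it matters only that power stays above the 80% target when each patient counts as one binary outcome. Nothing below uses 0.0948.

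**2. Inputs.** From the documents: 25 per arm, blocks of 4 to 10, manual mean 0.50. Assumed, because the documents are silent: two wards of 25 patients each; a ward gap in manual completeness of 0, 20, 40 or 60 points; within-ward patient SD 0.15 in the manual arm; FlowSure about 95% on both wards, with SD 0.05 or 0.15.

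**3. Chance imbalance, wards arriving in random order.** The number of patients from one ward in the manual arm has SD √(25 × 0.5 × 0.5 × 25/49) = 1.79, so its share has SD 1.79/25 = 0.071. The arms differ by 5 or more patients from a ward with probability 26% (hypergeometric, 25 of 50). Blocks that run across wards do not prevent this when ward order is random.

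**4. Effect on the estimate.** Shift = ward gap × (ward share in the manual arm − 0.5). Its mean is zero. Its SD is gap × 0.071: 1.4, 2.9 and 4.3 points for gaps of 20, 40 and 60.

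**5. Hand check of the standard error (FlowSure SD 0.05).**
- Stratified: √(0.15²/25 + 0.05²/25) = √0.0010 = 0.032.
- Unadjusted: √(0.0010 + (gap × 0.0714)²) = 0.035, 0.043 and 0.053 for gaps of 20, 40 and 60.

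**6. Simulation** with permuted blocks of 4, 6, 8 or 10, wards in random order and values truncated to 0–1, which lowers the hand figures a little:

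| Ward gap (points) | FlowSure SD 0.05: unadjusted vs stratified | FlowSure SD 0.15: unadjusted vs stratified |
|---|---|---|
| 0 | practically equal | practically equal |
| 20 | 0.034 vs 0.032 | 0.038 vs 0.036 |
| 40 | 0.041 vs 0.031 | 0.047 vs 0.037 |
| 60 | 0.050 vs 0.029 | 0.054 vs 0.034 |

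On unrounded figures, stratifying cuts the standard error by about 6–8% at 20 points and 20–25% at 40. At 60 points the cut is 1 − 0.029/0.050 = 42% or 1 − 0.034/0.054 = 37%. With no gap it costs about 1%. As 95% half-widths at FlowSure SD 0.05, 1.96 × SE is 6.7 vs 6.3 points, 8.0 vs 6.1, and 9.8 vs 5.7.

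**7. The interval that would be printed.** An unadjusted two-sample standard error on per-patient percentages also absorbs the between-ward spread: √((0.15² + (gap/2)²)/25 + 0.05²/25) = 0.037, 0.051 and 0.068. The simulated values are 0.037, 0.050 and 0.066. So the printed interval would be somewhat wider than the unadjusted column of the table implies.

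**8. Wards recruited one after the other.** The blocks then balance most of the wards by themselves. With FlowSure at 93% (SD 0.05) and manual SD 0.15 to 0.25, the SD of the shift falls to 0.6, 1.1 and 1.7 points. The unadjusted standard error is only 0–2%, 3–5% and 6–13% larger than the stratified one, against 3–9%, 14–34% and 29–69% with random order.

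**9. Effect on the test.** On per-patient percentages, even the largest unadjusted figures leave 0.40/0.054 = 7.4, or 0.40/0.066 = 6.1 with the printed standard error, far above 1.96.

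**The case against.** The strongest objection is that the documents do not contain the driver. Section 1 links missed readings to a nurse's time and other patients, not to ward. No section gives completeness, staffing or patient share by ward, and the same mechanism could point to shift or time of day. This stands: a ward effect is an inference, and every ward rate above is assumed.

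It also stands that the gain is slight up to a gap of about 20 points, that blocking already does most of the work if wards are recruited in turn, and that section 9.1 leaves room for regression. That last provision is optional, exploratory and silent on ward, so it does not settle the analysis in advance. Stratified randomisation is not obligatory in a single-hospital trial of 50, and section 4.1 allows further wards, so a two-way split must fit actual recruitment.

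A reader might infer more: that ward is the strongest predictor of completeness, that ward imbalance biases the comparison, or that it endangers the conclusion. The documents support none of these. They do not rank predictors. Under randomisation the shift averages zero, and the simulated mean difference was unbiased in every scenario. The planned 40-point difference is many times any standard error found here. The 26% chance of a marked imbalance should not be read as unconditional either: it presumes equal wards in random order.

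**Conclusion.** The point holds as a minor one about precision. The plan recruits across wards that probably differ in workload, names workload as the reason for incomplete manual registration, and then leaves ward out of both the allocation and the primary comparison.

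The loss runs from nothing (no ward gap), through 6–8% of the standard error (20 points) and 20–25% (40 points), to about 40% (60 points). These figures assume two equal wards arriving in random order, manual within-ward SD 0.15 and no ward gap with FlowSure. They shrink sharply if wards are recruited in sequence. The test result would rarely change. The case for acting is that the remedy costs almost nothing, even if ward turns out not to matter.

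**What to change.** - **Section 9.1:** pre-specify the Part B difference in mean per-patient completeness with its 95% CI, stratified by or adjusted for ward type (CCU/intensive against general). If stratified, weight the ward-specific differences by each ward type's share of Part B patients. Show completeness by arm within ward type.
- **Section 5, only if Part B has not started:** stratify the Castor blocks by the same two ward types, and state how any further ward is classified. If Part B is under way, leave allocation alone and fix the analysis before the data are examined; that secures most of the gain.

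**Cost:** one analysis term and one Castor setting. Unfinished blocks in two strata may leave the arms slightly off 25/25, and adjustment costs about 1% in standard error if ward has no effect. With 50 patients, more than two strata would be hard to justify.

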## 6. INVESTIGATIONAL PRODUCT

The automated FlowSure monitor is a digital hanging scale that continuously weighs urine production over time as urine flows through the urine catheter into the catheter bag underneath the patient's bed. The FlowSure visualizes the most recent hourly urine production on the screen of the device. Since the specific weight of urine is equal to water and thus one gram is equal to one millilitre, the increase in weight of the urine bag over time is a surrogate for urine production. FlowSure does not come into contact with the patient or

the patient's urine. The urine flows from the bladder through the catheter into the catheter bag under the patient's bed, while the catheter bag is attached to the FlowSure. Instead of attaching the urine bag to the bed, the urine bag is attached to the FlowSure, so that the weight can be continuously measured and recorded. Since the FlowSure does not come into contact with the patient or the urine, it is reusable after surface disinfection. The reusability will make FlowSure (cost) effective to operate.

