### 7.1 Study parameters/endpoints

#### 7.1.1 Main study parameter/endpoint

The primary outcome event in Part A will be the accuracy of urine measurement over two set time intervals (a nursing shift of 8 hours and a full 24-hours period) using manual monitoring and automated monitoring. The golden standard is the total urine production measured in a measuring cup by draining the collection bag in comparison with the new FlowSure device. The primary outcome in part B of the study will be the completeness of the hourly diuresis registration will be compared between the manual and automated measurement groups.

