### 7.2 Study procedures

[figure not shown]
In part A, patient with a urine catheter will be monitored using the current standard of care with a manual measuring chamber and a collection bag below the measuring chamber. See image below.

The study procedure in part A is that the manual monitor displayed above will be attached to the investigational FlowSure device. The study subjects will thus be monitored both with the manual monitor and with the investigational FlowSure device.

In part B, in half of the study subject the manual monitor will be replaced by investigational FlowSure device. These patients will receive a urine collection bag without a measuring chamber.

The urine collection bag has an approximate graduation scale, such that in case of device malfunction the nurse can read the urine production from the collection bag.

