#### e. Accuracy and reliability of device measurements:

Evaluating the accuracy and reliability of the device's measurements is paramount. In Part A of the study the investigation automated urine monitor FlowSure will be used in conjunction with standard manual urine production monitor. Patients will therefore be double monitored in Part A.

The protocol will transition to part B only when the investigational FlowSure device performance is within 15% difference from manual monitoring. In Part B of the study the investigational FlowSure device will replace the manual monitor. The nurse will be able to read the urine production manually from the urine collection bag (without the measuring chamber) as the bag is transparent with an approximate graduation scale.

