#### f. User training and competence:

Nurses who take care of a study subject will receive written instruction prior to working with the investigational FlowSure device in order to avoid improper use, incorrect interpretations of results, or failure to identify potential risks associated with the device.

g. Maintenance and calibration requirements:

After each deployment the investigational FlowSure device will be checked for adequate function and damage.

h. Environmental considerations:

The housing of the device is waterproof and fully reusable.

i. Potential for misuse or user error:

The potential for misuse or error are small. The software of the investigational FlowSure device is programmed to recognize when the collection bag is emptied by the nurse and simply asks them to confirm their action. If the bag is removed from the device for a period of time and then placed back, the device will recognize this and continue its measurements.

Incorrect measurements as a result of swinging of the urine collection bag is mitigated by the software algorithm through discarding large changes in subsequent measurements.

A potential for misuse is when the urine collection bag touches the ground and the bag does not hang on the device, the measurements are inadequate. Nurses are instructed to make sure that urine collection bag does not touch the ground.

j. Mitigation strategies and safety features:

If the investigations FlowSure device malfunctions or fails, the nurse can always revert back to reading the urine production manually from the urine collection bag (without the measuring chamber) as the bag is transparent with an approximate graduation scale.

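### In Part A nothing protects the manual chamber readings from the FlowSure screen value, so the 15% rule for starting Part B may be easier to meet than it looks

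*Combined protocol and SAP*

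**What the plan says.** Section 6 describes the display: "The FlowSure visualizes the most recent hourly urine production on the screen of the device". Section 1 describes the same screen and adds that the data go to the electronic medical record.

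Section 7.2 puts both monitors in one place for Part A: "The study procedure in part A is that the manual monitor displayed above will be attached to the investigational FlowSure device". It continues: "The study subjects will thus be monitored both with the manual monitor and with the investigational FlowSure device".

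On staff, section 1 says of usual care that "reading and registering diuresis manually every hour for every patient is burdensome for nurses and often deprioritized due to time constraints". Item f of the structured risk analysis (11.7) says: "Nurses who take care of a study subject will receive written instruction prior to working with the investigational FlowSure device". Item i adds that the device asks the nurse to confirm when the bag has been emptied.

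The manual reading is used in two ways:

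- **Part A primary outcome.** Section 7.1.1 sets accuracy over 8 and 24 hours "using manual monitoring and automated monitoring", with the measuring cup as reference. The Summary says explicitly that the manual and the automated monitor are each compared with the cup.
- **Rule for starting Part B.** Item e of 11.7 states: "The protocol will transition to part B only when the investigational FlowSure device performance is within 15% difference from manual monitoring". The comparator here is manual monitoring, not the cup.

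Section 3 calls Part B non-blinded. The readable text says nothing about masking the screen, a separate reader or the order of readings in Part A.

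**The concern.** When two methods are compared on the same patient, each reading should be taken without knowledge of the other. Here the chamber and a screen with an hourly figure hang together, and the protocol itself says that manual hourly reading is a task for which nurses lack time. Filling a missed hour from the screen, or settling a doubtful chamber level by looking at it, would be a natural shortcut, and nothing in the plan prevents it.

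Two results are exposed. The first is the 15% rule: if some manual values derive from FlowSure, part of the agreement is built in. The rule matters because in Part B the FlowSure arm loses the measuring chamber and keeps only a bag with an approximate scale. The second is the manual-versus-cup comparison in Part A: if FlowSure is close to the cup, manual values drawn towards FlowSure are also drawn towards the cup. Neither effect can be removed after the readings have been taken.

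**Working it through.** **The plan's own figure.** The 15% margin is stated without a calculation, unit (hour, shift, 24 hours, patient), statistic or confidence limit, so there is nothing to reproduce. The 25 patients in Part A (4.3) also come without a calculation.

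**Model (assumed).** Set the independent chamber value to 1 and let FlowSure read 1 + d. Suppose a fraction w of the manual record comes from the screen. The recorded manual value is then (1 - w) × 1 + w × (1 + d) = 1 + wd, and the observed difference relative to it is

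observed = (1 - w)d / (1 + wd).

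For under-reading by d, the observed size is (1 - w)d / (1 - wd). For any w between 0 and 1, both are smaller than d. The direction therefore does not depend on the value of w.

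**True difference that just meets the 15% rule.** Setting the observed value to 0.15 and solving for d gives:

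- over-reading: d = 0.15 / (1 - 1.15w)
- under-reading: d = 0.15 / (1 - 0.85w)

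| w (assumed) | Over-reading | Under-reading |
|---|---|---|
| 0 | 15.0% | 15.0% |
| 0.10 | 0.15/0.885 = 16.9% | 0.15/0.915 = 16.4% |
| 0.25 | 0.15/0.7125 = 21.1% | 0.15/0.7875 = 19.0% |
| 0.50 | 0.15/0.425 = 35.3% | 0.15/0.575 = 26.1% |

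The limit becomes as loose as 20% at w = (1 - 0.15/0.20)/1.15 = 0.22 for over-reading and 0.25/0.85 = 0.29 for under-reading. At w = 0.25 the two directions separate: a true +20% shows as 0.15/1.05 = 14.3% and passes, while a true -20% shows as 0.15/0.95 = 15.8% and fails.

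**Chance of passing.** This was simulated with 25 patients and 20,000 runs, passing if the relative difference in summed volume is at most 15%. The assumed per-patient SD is 10% for manual and 10% or 20% for FlowSure. With a true difference of +20%, the rule is met in 5% to 14% of runs at w = 0, 59% to 63% at w = 0.25, and at least 99.9% at w = 0.50.

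**Manual versus cup.** If FlowSure equals the cup, a manual error e is recorded as (1 - w)e: three quarters of its true size at w = 0.25 and half at w = 0.50.

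**FlowSure versus cup.** Neither quantity contains the chamber reading, so w does not enter.

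**The case against.** The strongest reply is that the main accuracy result is safe. The Part A reference is the cup, and FlowSure against the cup does not use the chamber reading. Section 7.6 adds a cup-based example for termination (deviation above 20%), and the bench test in 6.1 found FlowSure within 1%. The first point stands in full. The 7.6 example is a partial safeguard, but it is looser than 15% and does not replace the start rule. The bench test used one fixed flow rate, so it does not settle performance in patients; equally, nothing in the documents suggests an error as large as 20%.

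A reader might infer more than the text supports:

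- **That one nurse reads both values, or that the manual values are in fact dependent.** The Part A reader is not named. Section 1 describes usual care, and no copying is reported. The documents show only that independence is not protected.
- **That the 15% rule is too easy.** It has no unit or statistic, and missed or noisy manual readings could make it harder to meet, so its net stringency cannot be judged.
- **That the cup reading is contaminated too.** Only an hourly value is described on the screen, not a running total. Section 7.4 treats early disposal of the reference without a study investigator present as a deviation, which suggests that an investigator attends the cup measurement.
- **That up to half the manual record could be copied, because manual completeness is taken as about 50% (4.3 and 9.2).** That figure is an assumed rate of registered hours. It says nothing about how often a screen value is used instead.

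The figures in sections 7 and 7.2 were not available for this check. If one of them specifies masking or a reading order, the point is already met.

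**Conclusion.** The point holds in a limited form. As written, Part A leaves the chamber readings open to anchoring or copying. Any such dependence shrinks the FlowSure-manual difference, so it can only loosen the 15% rule. It would also make the manual monitor look better against the cup if FlowSure is accurate. It does not touch the FlowSure-versus-cup result.

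The direction follows from the algebra; the size does not follow from the documents. The ranges above rest on an assumed w, on a manual total built from hourly entries (7.1.1 does not say how it is formed), and on reading the 15% relative to the recorded manual value. They illustrate sensitivity and do not estimate bias. This is a low-cost protection worth adding before Part A enrols, not evidence that the start rule will be met wrongly.

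**What to change.** In 7.2, for Part A only:

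1. Require the chamber reading to be written down, with the time, before any FlowSure value is viewed, whether on the screen or in the record.
2. Cover or switch off the hourly value where this leaves the bag-emptying prompt usable. The documents do not say whether the device allows this; if it does not, item 1 still applies.
3. Take FlowSure values for the analysis from the device data afterwards.

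Alternatively or in addition, in 11.7 e, base the rule for starting Part B on the measuring cup, which the protocol already names as its gold standard. This removes the route from the start rule without any change to the device. The manual-versus-cup comparison would still need items 1 to 3.

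The cost is one procedural line and possibly a cover or display setting. Nurses would not see FlowSure values in Part A, where the manual monitor remains standard care.
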